9.3.1 Evaluable for toxicity

All participants will be evaluable for toxicity from the time of their first treatment with encaleret.

9.3.2 Evaluable for objective response

Not applicable.

9.3.3 Evaluable Non-Target Disease Response

Not applicable.

9.4 Statistical Analyses

9.4.1 General Approach

Categorical variables will be summarized by counts and percentages. Continuous variables will be summarized with descriptive statistics (n, mean, standard deviation, median, inter-quartile range etc.). All analyses will be performed using SAS 9.4 (the SAS Institute, Cary NC).

9.4.2 Analysis of the Primary Endpoints

The primary endpoint is the percent change in FECa from baseline to the last day on encaleret 162 mg BID. If a subject stops encaleret early or decreases the dose, the FECa will be calculated using the last fasting labs when the patient was on encaleret 162 mg BID. For this primary endpoint, if the normality assumption holds, one-sample t-test will be used to analyze the data. Otherwise, the nonparametric alternative, the Wilcoxon signed-rank test will be used.

The primary endpoint analysis will be conducted in the Treatment Population.

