4 STUDY DESIGN

4.1 Overall Design

This will be a single-site, open-label, phase 2, proof-of-principle study to evaluate the PTH-independent effects of encaleret on renal calcium handling in participants with hypocalcemia due to PSH.

Up to 30 participants may be enrolled to support up to 15 participants entering the treatment phase of the study. Two main cohorts are planned:

Cohort 1: Permanent PSH with neck surgery ≥ 12 months ago (minimum 7, up to 10 participants)

Cohort 2: Recent PSH with neck surgery < 12 months ago (up to 5 participants)

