9.2 Sample Size Determination

The proposed clinical trial is primarily exploratory and preliminary data is limited. The primary study endpoint is the percent decrease in FECa using the entire Treatment Population (all participants who received at least one dose of study drug). Participants withdrawing for any reason any time after receiving their first dose of the study drug will remain in the Treatment Population, and the final FECa used will be the last fasting timepoint during which the patient was taking encaleret 162 mg BID.

Power calculations were based on the prior experience with encaleret in ADH1. In the ADH1 cohort, during a 5-day dosage escalation study (period 1), when 6 subjects were on the maximal dose of 162 mg BID for 3 days, the Mean (Standard deviation) of the Day 6 change in fasting FECa from baseline was -66 (20) % (unpublished data). Using a two-tailed 0.05 level paired t-test, we found that 15 participants yielded 80% power to detect a percent change of 16%; 10 participants yielded 80% power to detect a percent change of 20% and 5 participants yielded 80% to detect a percent change of 34%. Given the mean reduction in FECa was 66% in the ADH1 cohort (and the kidneys of participants with PSH might be expected to respond even more robustly to encaleret), we anticipate even a sample size of 5 would be sufficient to confirm the proof-of-principle effect on FECa.

Nevertheless, we plan to enroll up to 15 participants in this study in order to increase the likelihood that we include participants with a range of residual parathyroid tissue and to include participants with recent hypoparathyroidism. This will allow for sub-group analysis (see Section 9.3), which will be exploratory and hypothesis generating.

Of note, we plan to enroll only 5 participants with recent PSH (Cohort 2), because we anticipate some challenges in enrolling this population. More than 5 participants may be impractical to enroll in a reasonable amount of time.

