9.4.7 Sub-Group Analyses

Due to small sample size and because this is a proof-of-principle study, primary and secondary endpoints will not be analyzed based on age, sex, race/ethnicity, or other demographic characteristics. Primary and secondary endpoints will be analyzed in each of the analysis populations listed in Section 9.3.

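### In populations of 5 or fewer, which always includes Cohort 2, the exact two-sided signed-rank fallback cannot reach p < 0.05 (a minor gap in the exploratory analyses)

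*Combined protocol and SAP*

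**What the plan says.** Section 9.4.2 analyses percent change in FECa with a one-sample t-test if normality holds. The alternative reads: "Otherwise, the nonparametric alternative, the Wilcoxon signed-rank test will be used". The section gives no criterion for judging normality, no minimum sample size, no choice between the exact and approximate versions of the test, and no alpha or sidedness. It places the primary analysis in the Treatment Population.

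Section 9.4.7 then says: "Primary and secondary endpoints will be analyzed in each of the analysis populations listed in Section 9.3". Cohort 2 is one of those populations, and Section 4.1 fixes its size: "Cohort 2: Recent PSH with neck surgery < 12 months ago (up to 5 participants". The PTH-Clamp, Aparathyroid, thyroid-status and thyroid-cancer populations have no minimum size.

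The only level and sidedness in the document are in the power calculation of Section 9.2: "Using a two-tailed 0.05 level paired t-test". That section takes its planning values from six ADH1 subjects and gives an 80%-power figure for 15, 10 and 5 participants. It concludes: "we anticipate even a sample size of 5 would be sufficient to confirm the proof-of-principle effect on FECa". It also calls the subgroup analyses exploratory.

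**The concern.** A signed-rank test on very few values has a coarse null distribution. If its smallest possible p-value is above 0.05, the test cannot reject, however large and consistent the effect. Cohort 2 can never exceed 5, so there the fallback would give the same answer for every data set, and the normality check alone would decide whether significance was possible. A consistent large fall in FECa could then be labelled non-significant and read as no renal effect in recent PSH. The same holds for any other Section 9.3 population that ends with 5 or fewer. The remark in Section 9.2 that 5 participants would suffice also covers only one branch of the analysis rule.

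**Working it through.** **Inputs.** Two-tailed alpha 0.05, mean change -66% and SD 20% (Section 9.2); Cohort 2 at most 5 and Cohort 1 between 7 and 10 (Section 4.1); the t-test with signed-rank fallback (Section 9.4.2).

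**1. The plan's own figures.** For a one-sample t-test, power at a true change d is approximately P(T > t(0.975, n-1)), where T is noncentral t with n-1 degrees of freedom and noncentrality (d/20) x sqrt(n). The opposite tail is negligible. Solving for 80% power:

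| n | Detectable change | Stated | Power at the stated change |
|---|---|---|---|
| 15 | 15.6% | 16% | 82.1% |
| 10 | 19.9% | 20% | 80.3% |
| 5 | 33.6% | 34% | 80.8% |

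The stated figures are the solutions rounded up, so they are right for the t-test. At n=5 and d=66, t-test power is 99.9%.

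**2. The floor of the fallback.** Under the null, each of the 2^n sign patterns is equally likely. The most extreme result is all changes in one direction, so the smallest exact two-sided p is 2/2^n:

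| n | Smallest p |
|---|---|
| 3 | 2/8 = 0.25 |
| 4 | 2/16 = 0.125 |
| 5 | 2/32 = 0.0625 |
| 6 | 2/64 = 0.031 |
| 7 | 2/128 = 0.016 |

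The test first becomes able to reject at n=6. At n=5 its power is 0% at any effect size.

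**3. Dependence on the version of the test.** With five falls out of five, the one-sided exact p is 1/32 = 0.031. For the normal approximation, the rank sum has null mean 5 x 6/4 = 7.5 and variance 5 x 6 x 11/24 = 13.75 (SD 3.71). Then z = 7.5/3.71 = 2.02 and p = 0.043 without continuity correction; with it, z = 7.0/3.71 = 1.89 and p = 0.059. Section 9.4.2 specifies none of these. An approximation is not reliable at n=5.

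**4. How often it would matter.** The plan names no normality check, so I assume Shapiro-Wilk at 0.05. At n=5 the whole procedure rejects only if the check passes and the t-test rejects, because the fallback never rejects. Results are from simulation with 20,000 samples per row; the ranges cover repeated runs.

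| Data, n=5 | Fallback used | t-test alone | Whole procedure |
|---|---|---|---|
| Normal, mean -34, SD 20 | about 5% | 81% | about 77% to 78% |
| Normal, mean -66, SD 20 | about 5% | 99.9% | about 95% |
| Lognormal ratio matched to -66 (20) | about 11% | 97% | about 87% to 88% |

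For the lognormal row, the ratio to baseline has mean 0.34 and SD 0.20. The log-SD is therefore sqrt(ln(1 + (0.20/0.34)^2)) = 0.545 and the median ratio is 0.34/sqrt(1 + (0.20/0.34)^2) = 0.293.

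**5. The primary analysis.** With the planned minimum of 7 in Cohort 1 alone, the floor is 0.016. For a 34% fall with normal data and SD 20, simulated signed-rank power is about 94% at n=7 and above 99% at n=10 and n=15.

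**The case against.** The strongest case against is that little depends on this. The primary analysis is in the Treatment Population, planned at up to 15, and the floor does not reach it. Section 9.4.7 names no test, level or decision rule for the subgroups, so applying the Section 9.4.2 rule there is an inference. Section 9.4.2 states neither alpha nor sidedness, and the hypothesis in Section 9.1 is directional; a one-sided exact test could reject at n=5. Section 9.2 already ties its power figures to a t-test, and the remark about 5 participants comments on margin and does not set the sample size. The summaries in Section 9.4.1, and the individual data that Section 9.4.8 allows, would show a uniform fall. Cohort 2 is included mainly to explore PTH secretion (Sections 2.1 and 4.2).

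Most of this stands, and it is why the point is minor. It does not remove the gap. Section 9.4.2 holds the only test rule given for this endpoint, and two-tailed 0.05 is the only level given, so the reading used here is the natural one. The outcome at n=5 also turns on an option that the plan leaves open.

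A reader might infer three stronger things, and the documents support none of them:
- That the primary result is at risk. It is not, at 7 or more participants.
- That the n=5 power figure is wrong. It reproduces for the test that Section 9.2 names.
- That Cohort 2 has no power. Zero power applies only after the fallback is triggered; over the whole procedure, power stays near 95% at a 66% fall with normal data.

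**Conclusion.** The point holds, as a minor one. An exact two-sided signed-rank test at 0.05 cannot be significant with 5 or fewer participants, so the fallback cannot work in Cohort 2 or in any other Section 9.3 population that small. At n=5, under the assumed Shapiro-Wilk switch, the cost in power is about 3 to 4 percentage points at a 34% fall and about 5 at a 66% fall with normal data, and about 9 to 10 with lognormal data matched to the planning values. The conclusion rests on three readings: the exact version of the test, the level and sidedness of Section 9.2, and the Section 9.4.2 rule carrying over to the subgroups. The size also rests on the assumed normality check and on the ADH1 mean and SD applying to PSH. The primary analysis and the sample size are not affected.

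**What to change.** In Sections 9.4.2 and 9.4.7, use the signed-rank test only in populations of at least 6, and state that it is exact and two-sided at 0.05. For populations of 5 or fewer, which always includes Cohort 2, report individual values and the mean percent change with a t-based 95% confidence interval, and draw no significance conclusion from the signed-rank test. In Section 9.2, add that the remark that 5 participants would suffice holds for the t-test only.

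This costs a few sentences and needs no new data or participants. The downside is that a t-interval from 5 or fewer values rests on a normality assumption that cannot usefully be checked. It will be least trustworthy when the values look clearly non-normal, so the individual values should be shown beside it. That is acceptable for analyses already labelled exploratory.

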9.4.3 Analysis of the Secondary Endpoint(s)

To analyze the proportion of participants who achieve a concomitant normal or elevated fasting blood calcium (albumin-corrected calcium >8.5 mg/dL) and a normal 24-hour urinary calcium level on encaleret (<250 mg/24 hours for women, <300 mg/24 hours for men) at any point between day 1 and day 5, the proportion along with its 95% confidence interval will be calculated using the exact binomial distribution.

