3 OBJECTIVES AND ENDPOINTS

OBJECTIVES	ENDPOINTS	JUSTIFICATION FOR ENDPOINTS
Primary		
Evaluate the PTH-independent effects of encaleret on renal calcium	Percent change in Fractional Excretion of Calcium (FECa) from baseline (Day -1) to the final day	FECa reflects the relationship between blood calcium and

OBJECTIVES	ENDPOINTS	JUSTIFICATION FOR ENDPOINTS
handling in participants with PSH.	of treatment (Day 6 or the last measurement while on encaleret). FECa calculated using fasting blood levels and spot urine collections.	urinary calcium. CaSR modulation by encaleret is expected to directly affect FECa. If a patient stops encaleret early prior to Day 6, the last fasting FECa on encaleret 162 mg BID will be used for this endpoint.
Secondary		
Evaluate the ability of encaleret to normalize blood calcium while maintaining a normal urinary calcium in participants with PSH.	Proportion of participants who achieve a concomitant normal or elevated fasting blood calcium (albumin-corrected calcium >8.5 mg/dL) and a normal 24-hour urinary calcium level (<250 mg/24 hours for women, <300 mg/24 hours for men) on encaleret at any point between day 1 and day 5.	Clinically relevant endpoint to determine if encaleret can allow PSH to have both normal blood and urinary calcium.
Tertiary/Exploratory		
Evaluate the ability of encaleret to increase serum iPTH levels in participants with PSH.	Change in blood iPTH comparing average baseline iPTH to average peak iPTH on encaleret. The average baseline iPTH will include all baseline iPTH levels from the screening visit, Day -1, and pre-dose on Day 1. The average peak iPTH will average the peak iPTH levels on every day the patient is on encaleret (days 1 to 5). An increase in iPTH will be	Averaging iPTH will prevent spurious excursions from impacting outcomes

OBJECTIVES	ENDPOINTS	JUSTIFICATION FOR ENDPOINTS
	considered clinically significant if there is an increase both by 50% AND by more than 10 pg/dL.	
Evaluate the effect of encaleret on 1-alpha hydroxylase action by measuring 1,25-(OH) ₂ Vitamin D levels.	Change in 1,25-(OH) ₂ Vitamin D on encaleret comparing the maximal level prior to receiving calcitriol (On Days 3-5) to baseline (Average of Day 1 Pre-dose levels). Increase will be considered significant if there is an increase of more than 50%. Participants who receive calcitriol prior to Day 3 will be excluded.	

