5 STUDY POPULATION

5.1 Inclusion Criteria

Participants must meet the following criteria for inclusion during screening:

1. Be able to understand and sign a written informed consent form, which must be obtained prior to initiation of study procedures.

2. Age \geq 18 years
3. Postmenopausal women are allowed to participate in this study:
 - a. Women are considered postmenopausal and not of childbearing potential if they have had 12 months of natural (spontaneous) amenorrhea with an appropriate clinical profile (e.g., age appropriate, history of vasomotor symptoms) or have had surgical bilateral oophorectomy (with or without hysterectomy) or tubal ligation at least 6 weeks prior to start of the study. In the case of oophorectomy alone, only when the reproductive status of the woman has been confirmed by follow up hormone level assessment, shall she be considered not of childbearing potential.
4. Body mass index (BMI) \geq 18.5 to $<$ 39 kg/m²
5. Have a diagnosis of PSH, either permanent PSH (Cohort 1, surgery \geq 12 months ago) or recent PSH (Cohort 2, surgery $<$ 12 months ago).
6. Participants must have achieved an albumin-corrected blood calcium level of 7.8-10.2 mg/dL on conventional therapy without significant symptoms of hypocalcemia or hypercalcemia.
7. Participants being treated with thiazide diuretics may be enrolled if they are willing and able to discontinue thiazides for at least 5 half-lives prior to initiation of encaleret and remain off during the study treatment period. (5 half-lives of hydrochlorothiazide = 75 hours; chlorothiazide = 10 hours; chlorthalidone = 12.5 days). If the thiazide is being used as an antihypertensive, as opposed to use as a urine calcium-lowering drug, alternative therapy will be offered.
8. Participants being treated with strong CYP3A4 inhibitors (including clarithromycin, telithromycin, nefazodone, itraconazole, ketoconazole, atazanavir, darunavir, indinavir, lopinavir, nelfinavir, ritonavir, saquinavir, tipranavir) may be enrolled if they are willing and able to discontinue these medications for at least 5 half-lives prior to initiation of encaleret and remain off during the study treatment period.
9. Participants being treated with magnesium or potassium citrate supplements should discontinue such treatment starting on Day -2.

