6.1.2 Dosing and Administration

On Day -1/-2, participants who met eligibility criteria at the screening visit will be admitted to the NIH CC. Participants will not take their magnesium and potassium citrate starting on the morning of Day -2. Participants will not take their standard-of-care calcium or calcitriol starting on the morning of Day -1, and will instead start a personalized calcium supplementation, determined by investigators from their baseline calcium requirements and levels. They will start on a dietary daily calcium intake of approximately 1000 mg per day, which may be adjusted if needed.

Encaleret 162 mg twice a day will be administered to participants on Day 1 to 5. Additional calcium and/or calcitriol will be administered per algorithm (Table D) if required.

Calcium and calcitriol supplementation will be adjusted following the algorithm delineated in Table D with the primary goal of safety. Mild to moderate symptomatic hypocalcemia at any calcium level, cCa < 7 mg/dL, or borderline QT prolongation, would cause investigators to give oral calcium and/or calcitriol. Doses will be determined at the discretion of experienced investigator's understanding of the patient's prior supplement requirements and severity of hypocalcemia. IV calcium may be used for participants with severe hypocalcemic symptoms or QTcF > 500 ms. If a patient develops mild hypercalcemia, then calcium and calcitriol will be held until cCa is less than 9 mg/dL. If cCa has not trended down by 12 hours (or earlier per investigator discretion), encaleret will be stopped. If cCa is > 12 mg/dL, encaleret will be discontinued and calcium and calcitriol will be held until cCa is < 9 mg/dL, when home regimen is restarted.

On Day 3, investigators will add calcitriol supplementation if the albumin-corrected calcium remains < 8.5 mg/dL. The calcitriol dose will be determined by investigators, taking into account the current calcium level and the subject's baseline requirements.

The last dose of encaleret will be given on the night of Day 5. The patient will then resume calcium and calcitriol and be discharged home. If the patient is hypercalcaemic or hypocalcemic, their baseline calcium and calcitriol may be adjusted at discharge. If needed, they may remain at the NIH clinical center until their labs have stabilized to a safe level.

Table D: Titration algorithm:

		Encaleret Titration	Calcium supplementation titration*	Calcitriol titration*	Additional interventions/ monitoring

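### The any-day secondary endpoint has no off-drug comparator and does not separate successes reached after calcitriol, so its proportion cannot be attributed to encaleret alone

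*Combined protocol and SAP*

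**What the plan says.** Section 3 states the secondary objective as normalising blood calcium while urinary calcium stays normal. Under Section 9.4.3 a participant succeeds who can "achieve a concomitant normal or elevated fasting blood calcium (albumin-corrected calcium >8.5 mg/dL") together with 24-hour urinary calcium below 250 mg (women) or 300 mg (men). The window and analysis are: "at any point between day 1 and day 5, the proportion along with its 95% confidence interval will be calculated" from the exact binomial distribution. The plan gives no null value, alpha or comparison with baseline for this endpoint.

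Four other places bear on it:

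- **Calcitriol.** Section 6.1.2: "On Day 3, investigators will add calcitriol supplementation if the albumin-corrected calcium remains < 8.5 mg/dL". Table D adds that rescue calcitriol may be given earlier.
- **Entry.** Section 5.1, criterion 6: "Participants must have achieved an albumin-corrected blood calcium level of 7.8-10.2 mg/dL on conventional therapy". Hypercalciuria is not an entry requirement.
- **Wording of the window.** The synopsis (Section 1.1) and Section 3 put "on encaleret at any point between day 1 and day 5" after both components. In Section 9.4.3 the words about being on encaleret follow the urine component only.
- **Early stopping.** Under Drug Discontinuation in Section 6.1.2, meeting this endpoint (high calcium allowed) is one of two conditions for discretionary early discontinuation. The other is a fall in fasting FECa of more than 40%.

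**The concern.** The study is single-arm and open-label, so the proportion has to carry its own reference. As defined, it combines several things besides the drug:

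- **Several chances.** With complete data, the any-day proportion can never be below the proportion on any one of those days.
- **A second calcium-raising drug at the same cut-off.** Those who fail the blood component by Day 3 are the ones given calcitriol, inside the endpoint window. The exploratory 1,25-(OH)₂ vitamin D endpoint guards against this: it uses the maximum before calcitriol and excludes anyone given calcitriol before Day 3. The secondary endpoint has no such rule.
- **Status before treatment.** Someone already inside both limits before the first dose can count as a success.
- **No ceiling.** A participant with cCa above 12 mg/dL, for whom Table D discontinues encaleret, still meets the blood component, although the objective speaks of normalising calcium.

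Section 3 presents the endpoint as clinically relevant for judging whether encaleret allows both values to be normal. A high proportion would be read as that answer. The exact interval covers sampling error only and none of the points above.

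**Working it through.** **1. The plan's own figures.** The plan gives no expected rate or power for this endpoint. Its only power statement (Section 9.2) concerns FECa: SD 20%, two-sided 0.05 paired t-test, 80% power. Solving the noncentral-t power equation (n−1 degrees of freedom, noncentrality δ√n/20) gives detectable changes of 15.56% (n=15), 19.92% (n=10) and 33.64% (n=5). These reproduce the stated 16, 20 and 34% after rounding up. They do not bear on this point.

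**2. Which blood goes with which urine.** Table B runs each 24-hour urine from after the first morning void to the next morning. Table C gives the fasting draws.

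| 24-hour urine | Fasting draw at its close | Status |
|---|---|---|
| Day −1 | Day 1, −30/−15 min | before first dose |
| Days 1 to 4 | next day, −15 min | on drug |
| Day 5 | Day 5 row, 24-hour column | on drug |

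Every specimen for one off-drug and five on-drug pairs is already scheduled. Pairing by calendar label instead would join the Day 1 urine, collected on drug, to a Day 1 fasting blood taken before any encaleret. The plan does not say which pairing it intends.

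**3. Illustrative effect of the any-day rule.** Let p be the chance of meeting both limits on one day, whatever the cause, equal on all days. Let ρ be the latent between-day correlation within a participant. The documents give neither, so both are assumptions.

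- Independent days: P(any of k) = 1 − (1 − p)^k. For p = 0.20, k = 5: 1 − 0.8⁵ = 0.672. For p = 0.30: 1 − 0.7⁵ = 0.832.
- Correlated days (exchangeable Gaussian copula): average 1 − (1 − q(u))^k over a standard normal u, with q(u) = Φ[(z_p − √ρ·u)/√(1 − ρ)], where z_p is the normal quantile of p.

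| Single day | Any of 5, ρ=0.9 | ρ=0.8 | ρ=0.5 | independent |
|---|---|---|---|---|
| 20% | 31% | 37% | 49% | 67% |
| 30% | 44% | 50% | 63% | 83% |
| 50% | 65% | 71% | 83% | 97% |

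Removing one day (k = 4) at p = 0.20 gives 29.8% against 31.3% at ρ = 0.9, and 59.0% against 67.2% with independence. Under these equal-day assumptions the Day 1 question is worth about 1.5 to 8 points. Residual home therapy on Day 1 could make it larger.

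**4. What this does to the interval at n = 15.** Expected counts at p = 0.20 are 15 × 0.20 = 3 (single day), 15 × 0.313 = 4.7 (any day, ρ = 0.9) and 15 × 0.672 = 10.1 (any day, independent). Exact 95% intervals: 3/15, 4.3–48.1%; 5/15, 11.8–61.6%; 10/15, 38.4–88.2%.

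**The case against.** The strongest defence is that this is a descriptive summary in a small proof-of-principle study, with no hypothesis or threshold attached. Absolute levels and change from baseline in cCa and 24-hour urinary calcium are already exploratory endpoints. The background section asks whether encaleret could be standalone or adjuvant therapy, so success with calcitriol is of interest. Calcitriol alone does not make a responder, because urinary calcium must also be normal and Section 2.1 says conventional therapy often causes hypercalciuria. Accepting elevated calcium is explicit and fits the rationale that urinary calcium may fall even when blood calcium is high. Entry calcium is measured on conventional therapy, and home calcium and calcitriol stop after Day −2.

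Much of this stands. It argues against scoring every calcitriol recipient as a failure, imposing a calcium ceiling or dropping the any-day figure. It does not remove the need for an off-drug value of the composite, which separate component summaries do not supply, or for showing which successes preceded calcitriol.

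Four stronger readings are tempting but unsupported:

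- **That the Day 1 pre-dose calcium is counted.** Section 9.4.3 leaves it open, but Sections 1.1 and 3 can be read as requiring both components on drug. It is an ambiguity.
- **That the draw closing the Day 5 urine is outside the window.** Table C lists it in the Day 5 row.
- **That the proportion says nothing about encaleret.** The 24-hour urines on Days 1 to 5 are collected on drug.
- **That inflation changes the trial's conclusion.** The contrast of 3/15 with 10/15 needs independent days, which is implausible for consecutive inpatient days. Even then the intervals overlap, and the plan sets no threshold to cross.

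**Conclusion.** The concern holds in a limited form. The proportion cannot be attributed to encaleret alone, for three reasons: there is no off-drug value of the composite, successes after calcitriol are not separated, and the blood–urine pairing is unspecified. It is also biased upward relative to a fixed-day measure. The direction follows from the definition, but the size cannot be derived from the documents. Under the assumed range (single-day chance 20–30%, correlation from 0.9 down to independence) the excess over one fixed day runs from 11 points (31% against 20%) to 53 points (83% against 30%). The lower end is more plausible for consecutive inpatient days. The plan's interval is correctly calculated for the quantity it describes. The weakness lies in what that quantity can be taken to show.

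**What to change.** These are changes to analysis and reporting. No change to calcitriol, calcium or stopping rules is proposed.

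1. **Off-drug comparator.** Report the same composite from the Day −1 24-hour urine and the Day 1 pre-dose fasting cCa, naming which of the two pre-dose draws is used. Show the paired off-drug against on-drug table with an exact McNemar result, using one on-drug day (the last complete 24 hours), since setting any of five days against one off-drug day would bring the bias back. Treat it as descriptive: with six discordant pairs all in one direction the two-sided p is 2 × (1/2)⁶ = 0.031, and with five it is 0.063. State that this comparator may still carry home calcitriol taken up to Day −2.
2. **Pairing.** Pair each on-drug 24-hour urine with the fasting cCa at its close. Day 1 pre-dose blood then cannot count as on drug, and the Day 5 24-hour draw is used.
3. **Calcitriol.** Report successes reached before any calcitriol or IV calcium separately from those after it, following the logic of the 1,25-(OH)₂ vitamin D endpoint. Increased oral calcium remains a confounder and should be tabulated beside these.
4. **Several views.** Beside the any-day figure, report the last complete on-drug 24 hours and each day. Show separately successes with cCa above 10.2 mg/dL (the limit in Table D) and participants stopped early for achievement, whose last on-drug day may lie close to their success day.

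All specimens are already scheduled, so the cost is analysis time and aligned wording in Sections 1.1, 3 and 9.4.3. The early-discontinuation text in Section 6.1.2 refers to the same endpoint and should be checked for consistency. The attributable proportion will probably be lower than the any-day figure.
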